SUBJECT SELECTION CRITERIA	
Inclusion Criteria: > 18 years of age, Patients with moderate-severe psoriasis or atypical psoriasis with either non-biologic treatment failure or > 5% body surface area affected.
 
Exclusion Criteria: tuberculosis, active serious infection, active systemic malignancy, or received a systemic medication for psoriasis within 3 months of study screening.

TEST PRODUCT, DOSE, AND ROUTE OF ADMINISTRATION	Tildrakizumab 100 mg subcutaneous injection
CONTROL PRODUCT, DOSE AND ROUTE OF ADMINISTRATION	n/a

DURATION OF SUBJECT PARTICIPATION AND DURATION OF STUDY	
The time commitment for the first visit will be approximately 1.5 hours to discuss the study, consent the patient, and perform the biopsy.
 
The second visit will last approximately 15 minutes
 
The third and fourth visits will last approximately 30 minutes.
 
With a total time committment of ~ 2 hrs 45 minutes

CONCOMMITANT MEDICATIONS	
Allowed:
 
Prohibited: other systemic medications for psoriasis

EFFICACY EVALUATIONS	
PRIMARY ENDPOINT	
 molecular gene expression profiling of skin cell populations.
SECONDARY ENDPOINTS	
 Psoriasis Area and Severity Index (PASI) score
OTHER EVALUATIONS	
SAFETY EVALUATIONS	
Re-evaluation of biopsy site at follow-up visit in 14 days for wound infection
 
In person medical visit for physical exam and history 4 weeks and 16 weeks after start of medication

PLANNED INTERIM ANALYSES	
When approximately 50% of patients have completed the study through Visit 4, an interim analysis for safety will be conducted by the investigator. Serious adverse events will be monitored by the committee on an ongoing basis throughout the study.

STATISTICS Primary Analysis Plan	
We will rely heavily on RNA-seq analysis, in some cases complemented with DNA sequencing and protein assessments. The RNAseq data will be normalized and compared in diseased vs normal skin and differential expression discerned at a significance level of 5% in a single test, in a two-group comparison, using a Negative Binomial mode. Numerous qualitative analyses will be performed as well.

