4 STUDY DESIGN

4.1 Study Overview

This is a single center study in which patients with psoriasis or atypical psoriasis will donate small samples of that skin and/or normal tissue prior to treatment with the FDA-approved psoriasis medication, tildrakizumab.

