9 EVALUATIONS BY VISIT

9.1 Visit 1

1. Review the study with the subject (subject's legal representative) and obtain written informed consent and HIPAA authorization and assent, if appropriate.
2. Assign the subject a unique screening number.
3. Record demographics data.
4. Record medical history, including a history of rash, diagnosis date, and prior treatments.

5. Record concomitant medications.
6. Perform a complete skin examination.
7. Clean skin, anesthetize skin, take skin sample(s) (up to 2 6 mm punch biopsies), place suture.
8. Photograph of biopsied lesional skin and other psoriatic lesions
9. Part of the biopsied specimen will be sent for standard histopathology (if no previous histopathology from a similar representative lesion has been done)
10. Schedule subject for suture removal in 14 days.
11. Baseline routine bloodwork (CBC, quant gold, HIV, HB surface Ag, Anti-HB surface AB, anti-HB core AB, hepatitis C antibody, BUN/Creatinine, AST/ALT)

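### The lesional-versus-normal comparison has no patient term, although any normal skin collected comes from the same patients who give lesional skin

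*Combined protocol and SAP*

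**What the plan says.** - **Contrast and model.** The synopsis states: "The RNAseq data will be normalized and compared in diseased vs normal skin". The test is to be made at 5%, "in a two-group comparison", with a Negative Binomial model. No patient factor, random effect, matching or clustering is mentioned there or elsewhere. Section 13.3 names only a generic distribution-based test and does not say which groups are compared.
- **Source of tissue.** Section 6.1 limits the study to psoriasis or atypical psoriasis, the synopsis lists no control product, and no healthy-donor cohort is described. Under section 4.1, patients "will donate small samples of that skin and/or normal tissue prior to treatment".
- **Biopsies per patient.** Section 9.1 has the investigator "take skin sample(s) (up to 2 6 mm punch biopsies") at Visit 1, without saying which tissue each biopsy should be.
- **Numbers.** The synopsis gives 10 subjects. Section 13.6 gives 10 samples and says that two-fold differences will be detectable, with no dispersion, power or split between tissues.

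**The concern.** Two skin samples from one person share genetics, treatment history and handling, so their expression levels are likely to be positively correlated. A one-factor two-group model leaves that shared variation in the error term. The estimated fold change is still sound, but its standard error is overstated, the nominal 5% test rejects less often than 5% under the null, and real differences can be missed. In a pilot of 10 patients whose size is limited by the cost of profiling, precision that one model term could recover is worth having. The plan also does not say how many matched pairs there will be, so the reader cannot judge how much this matters.

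**Working it through.** **The plan's own figure.** The section 13.6 claim (10 samples, two-fold) can be neither reproduced nor refuted, because no dispersion, read depth, power or group split is given. Under an unpaired two-sided 5% test (normal approximation), 80% power for a two-fold change needs a log-scale SD of at most 0.39 with 5 versus 5 samples, or 0.55 with 10 versus 10.

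**Inputs from the documents.** Two-fold change, so δ = ln 2 = 0.693; 5% level (sidedness not stated, two-sided assumed); 10 subjects and up to two biopsies each, so at most 10 pairs; 10 samples, so at most 5 pairs if that total is taken literally.

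**Assumptions, not in the documents.** Mean count μ = 100; total dispersion φ = 0.4, with 0.1 as a lower alternative; within-patient correlation ρ on the log scale from 0 to 0.7. Log-normal data stand in for Negative Binomial counts.

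**Formulas, n pairs.**
- SD = √(1/μ + φ) = √(0.01 + 0.4) = 0.640
- Unpaired standard error = SD·√(2/n), with 2n − 2 degrees of freedom
- True standard error of the difference = SD·√(2(1 − ρ)/n); the paired test has n − 1 degrees of freedom
- Ratio of true to unpaired standard error = √(1 − ρ): 0.84, 0.71 and 0.55 at ρ = 0.3, 0.5 and 0.7

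**One case in full: n = 10, ρ = 0.5.** Unpaired standard error = 0.640 × √0.2 = 0.286. True standard error = 0.286 × 0.707 = 0.202. Paired noncentrality = 0.693/0.202 = 3.4, against a critical value of 2.262 on 9 df, which gives 86% power. The unpaired t-test applied to the same correlated data (by simulation) gives about 67%.

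**Results at φ = 0.4.** Paired power is from the noncentral t; unpaired size and power are simulated on paired data.

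| Pairs | ρ | True size of unpaired 5% test | Power, unpaired | Power, paired |
|---|---|---|---|---|
| 10 | 0 | 5% | 63% | 58% |
| 10 | 0.3 | 2.3% | 65% | 73% |
| 10 | 0.5 | about 1% | 67% | 86% |
| 10 | 0.7 | 0.2% | 70% | 97% |
| 5 | 0 | 5% | 33% | 26% |
| 5 | 0.3 | 2.6% | 31% | 35% |
| 5 | 0.5 | 1.4% | 30% | 45% |
| 5 | 0.7 | 0.5% | 29% | 65% |

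With 5 pairs the two analyses break even near ρ = 0.2 (31% each).

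**Lower dispersion, φ = 0.1** (SD = √0.11 = 0.332). With 10 pairs both analyses exceed 99% power at ρ = 0.3 to 0.7. With 5 pairs, unpaired against paired power is 85% against 83% at ρ = 0.3, and 87% against 93% at ρ = 0.5.

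**The case against.** Several stronger readings are tempting, and the documents do not support them.

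- **That the plan specifies independent groups.** It does not say so. A two-group Negative Binomial model can carry a patient term. The defect is that the term is missing from the description.
- **That pairs will exist.** Sections 4.1 and 9.1 allow them but do not require them, and 10 samples from 10 subjects may mean one biopsy each. This objection stands, and it makes the size of the problem conditional. But with one biopsy each, any normal sample would come from a patient who gives no lesional sample for the responder question, so the tissue allocation needs stating in either case.
- **That false positives are inflated.** With positive correlation the error runs the other way.
- **That power is always lost.** It is not: with few pairs and low correlation, pairing spends degrees of freedom for little or no return.
- **That two lesional biopsies from one patient will be counted as separate samples in a responder comparison.** Nothing plans this. The documents are merely silent on how two such samples would be combined.

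It can also be said that section 13 promises a detailed SAP, which is the usual place for a blocking term, and that the primary objective in section 3.1 is a between-patient contrast of responders with non-responders. Both are fair. The first is only a partial answer, because tissue is chosen at Visit 1 and the sampling rule cannot wait for a later document. The second limits the importance of the point without removing it, since lesional versus normal is the only contrast for which the protocol names a model.

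**Conclusion.** The point holds as an omission with a conditional cost. The protocol's one named model has no patient term, while its sampling allows matched lesional and normal skin from the same person. For any such pairs, the comparison as written is conservative when the within-patient correlation is positive.

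At dispersion 0.4 the power given up at correlations of 0.3, 0.5 and 0.7 is about 8, 19 and 27 percentage points with 10 pairs, and about 4, 15 and 36 points with 5 pairs. At dispersion 0.1 it is negligible with 10 pairs, and with 5 pairs it is slightly reversed at correlation 0.3. At zero correlation the paired analysis is 5 to 7 points worse at dispersion 0.4. All of these figures rest on assumed mean count, dispersion and correlation and on a log-normal approximation; only the direction of the standard-error effect follows from the design. The change is worth making because it is cheap, but it is not a threat to validity.

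**What to change.** In the synopsis and section 13.3, include patient in the Negative Binomial model for the lesional-versus-normal comparison: a blocking factor (patient plus tissue type) if every contributing patient gives both tissues, or a random patient effect if some give only one. State in sections 4.1, 9.1 and 13.6 how many patients will supply both tissues, and reconcile that with the 10 samples. As a safeguard, specify one lesional profile per patient in any responder comparison, for example by summing counts if two lesional biopsies were taken.

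The cost is one model term and a few sentences. Degrees of freedom are lost (9 instead of 18 with 10 pairs, 4 instead of 8 with 5), which can lower power somewhat if correlation is low and pairs are few. With a blocking factor, patients with a single tissue type add nothing to the paired contrast, but those with lesional skin remain available for the responder analysis. The responder-versus-non-responder objective still needs its own analysis specification.

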1 BACKGROUND

Cutaneous inflammation represents the most common skin pathology, placing pervasive burdens on health care cost and quality of life. Biologic immunomodulatory therapies now enable improvement of major rashes such as psoriasis and atopic dermatitis; however, a significant minority of patients do not adequately respond to these medications. Given the multiple medication options that target different inflammatory pathways, significant expense and serious side effects of these immunomodulatory medications, it is imperative that we develop mechanisms to better predict whether a patient will respond to a given drug.

1.1 Overview of Non-Clinical Studies

1.1 We will be collecting skin tissue from psoriatic patients for the purposes of analyzing gene activity in these samples.

1.2 Overview of Clinical Studies

Patient will be assessed for improvement in their psoriasis using the Psoriasis Area and Severity Index (PASI) score. Patients will be administered tildrakizumab (a FDA-approved medication for psoriasis) following manufacturer's and FDA indications and dosing schedule.

2 STUDY RATIONALE

The researchers want to find a way to predict whether a person with psoriasis will respond to a given medication. In this study, patient will start tildrakizumab (a FDA-approved medication for psoriasis). Prior to treatment, a small piece of psoriasis-affected skin will be sampled and molecularly profiled. We will then analyze the molecular profiles and compare to patient tildrakizumab treatment response to predict which future patients will best respond to this medication.

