6	SUBJECT SELECTION	9
6.1	Study Population	9
6.2	Inclusion Criteria	9
6.3	Exclusion Criteria	9
7	CONCURRENT MEDICATIONS	9
7.1	Allowed	10
7.2	Prohibited	10
8	STUDY TREATMENTS	10
8.1	Method of Assigning Subjects to Treatment Groups	10
8.2	Blinding	10
8.3	Test and Control Formulation	10
8.4	Supply of Study Medication at the Site	10
8.5	Study Medication Accountability	11
8.6	Measures of Treatment Compliance	11
9	STUDY PROCEDURES AND GUIDELINES	11
9.1	Clinical Assessments	11
9.2	Pharmacokinetic Measurements	12
10	EVALUATIONS BY VISIT	12
10.1	Visit 1	12
10.2	Visit 2 (2 weeks after Visit #1)	12
11	ADVERSE EXPERIENCE REPORTING AND DOCUMENTATION	13
11.1	Adverse Events	13
11.2	Serious Adverse Experiences (SAE)	14
11.3	Medical Monitoring	15

- 12 DISCONTINUATION AND REPLACEMENT OF SUBJECTS15**
 - 12.1 Withdrawal of Subjects15
 - 12.3 Replacement of Subjects15
- 13 PROTOCOL VIOLATIONS15**
- 14 STATISTICAL METHODS AND CONSIDERATIONS16**
 - 14.1 Data Sets Analyzed16
 - 14.2 Demographic and Baseline Characteristics16
 - 14.3 Analysis of Primary Endpoint16
 - 14.4 Analysis of Secondary Endpoints16
 - 14.5 Interim Analysis16
 - 14.6 Sample Size and Randomization16
- 15 DATA COLLECTION, RETENTION AND MONITORING16**
 - 15.1 Data Collection Instruments16
 - 15.2 Data Management Procedures17
 - 15.3 Data Quality Control and Reporting17
 - 15.4 Archival of Data17
 - 15.5 Availability and Retention of Investigational Records17
 - 15.6 Monitoring18
 - 15.7 Subject Confidentiality18
- 16 ADMINISTRATIVE, ETHICAL, REGULATORY CONSIDERATIONS18**
 - 16.1 Protocol Amendments18
 - 16.2 Institutional Review Boards and Independent Ethics Committees18
 - 16.3 Informed Consent Form19
 - 16.4 Publications19
 - 16.5 Investigator Responsibilities20

LIST OF ABBREVIATIONS

none

PROTOCOL SYNOPSIS

TITLE	PREDICTING TREATMENT RESPONSE FOR INFLAMMATORY SKIN DISEASE
SPONSOR	self
FUNDING ORGANIZATION	none
NUMBER OF SITES	1
RATIONALE	To develop a predictive algorithm to determine whether a given patient with psoriasis will respond to one of the multiple specific pathway blocking FDA-approved psoriasis biologic medications.
STUDY DESIGN	interventional trial with molecular profiling of skin samples
PRIMARY OBJECTIVE	To obtain pre-treatment psoriatic skin samples for molecular profiling prior to treatment with tildrakizumab to correlate with and to predict treatment response
SECONDARY OBJECTIVES	
NUMBER OF SUBJECTS	10

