3 STUDY OBJECTIVES

3.1 Primary Objective

Our primary objective is to identify the genes that are differentially expressed in psoriatic skin between patients that do and do not respond to tildrakizumab

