13.1 Data Sets Analyzed

All eligible patients who consent to the study and have a skin sample taken will have data analyzed.

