13.3 Analysis of Primary Endpoint

After RNA sequencing performs, standard distribution-based statistical test for significantly overexpressed or under-expressed genes will be applied.

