13.6 Sample Size and Randomization

10 samples will be collected for initial analysis. Distribution-based statistical analysis indicates that two-fold differences in gene transcription will be detected at this size.

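### The synopsis and Section 2 promise prediction of response in future patients, but the plan only tests genes in one set of 10 patients and never evaluates prediction

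*Combined protocol and SAP*

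**What the plan says.** **Prediction wording.** The Rationale line of the Protocol Synopsis is "To develop a predictive algorithm to determine whether a given patient with psoriasis will respond" to one of several approved biologics. The synopsis primary objective is to profile pre-treatment skin both to correlate with response and to predict it. Section 2 says the profiles will be analysed and used to "compare to patient tildrakizumab treatment response to predict which future patients will best respond to this medication".

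**Association wording.** Section 3.1 is narrower: "identify the genes that are differentially expressed in psoriatic skin between patients that do and do not respond to tildrakizumab". Section 5.1 likewise asks only whether genes are up- or downregulated in specific cell populations, with PASI used to assess improvement.

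**Analysis.** Section 13.3 says that a "standard distribution-based statistical test for significantly overexpressed or under-expressed genes will be applied". The synopsis Statistics entry gives "differential expression discerned at a significance level of 5% in a single test, in a two-group comparison, using a Negative Binomial mode", for data "compared in diseased vs normal skin", and adds qualitative analyses that it does not describe. Section 13.1 forms one analysis set: "All eligible patients who consent to the study and have a skin sample taken will have data analyzed". Section 13.6 states "10 samples will be collected for initial analysis" and says that two-fold differences in transcription will be detected at that size.

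**Context.** The synopsis entry on the number of subjects calls the study a pilot, kept small because of profiling cost. It cites about 100 patients for bulk RNA-seq markers and expects that single-cell data may need fewer. Section 13 promises a detailed SAP before the final data are analysed.

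No classifier, gene-selection rule, held-out patients, cross-validation or accuracy measure appears in the current text.

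**The concern.** Finding genes whose expression differs between responders and non-responders is one task. Showing that those genes classify the next patient correctly is another, and it needs patients who played no part in choosing the genes, or a resampling scheme that imitates this. The plan states the second aim and describes only the first analysis.

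With thousands of genes and 10 patients, some genes will line up with response by chance. If the study closes by describing a gene list as predictive, nothing planned would tell a reader whether the list carries information about a new patient. The stated conclusion would be unsupported whatever the data show.

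**Working it through.** **1. The plan's own figure.** The two-fold claim in Section 13.6 cannot be reproduced: power, dispersion and group split are not given. As an approximation, on the natural-log scale with large counts and a 5/5 split, power = Φ(ln 2 / (CV × √(1/5 + 1/5)) − 1.96) at two-sided, unadjusted 5%.

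- CV 0.39 (assumed): 0.693/0.247 − 1.96 = 0.85, power 80%.
- CV 0.5: 0.693/0.316 − 1.96 = 0.23, power 59%.
- CV 1.0: 0.693/0.632 − 1.96 = −0.86, power 19%.

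Even where the claim holds, it concerns detecting an expression difference and says nothing about accuracy in new patients.

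**2. Chance separation.** Inputs: 10 patients (synopsis and Section 13.6). The number of genes, their independence and the response split are assumptions, since the documents give none of them. For one null gene, the chance that all values in one group lie above all values in the other is 2/C(10,k), where k is the size of the smaller group.

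| Split | 2/C(10,k) | Expected, 20,000 genes | Expected, 5,000 genes |
|---|---|---|---|
| 5/5 | 2/252 = 0.0079 | 159 | 40 |
| 7/3 | 2/120 = 0.0167 | 333 | 83 |
| 8/2 | 2/45 = 0.0444 | 889 | 222 |

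Real genes are correlated, so the effective number is smaller. Even 1,000 independent null genes give 1 − (1 − 2/252)^1000 = 99.97% chance of at least one perfect separator at 5/5, and more at the other splits.

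**3. What a signature would score under pure noise.** Simulated data: 10 patients, 20,000 independent noise genes, top 10 genes by t-statistic, nearest-centroid rule; 200 data sets, 60 for leave-one-out. Entries are mean balanced accuracy, for which chance is 50%.

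| Split | Same 10 patients | Leave-one-out, genes chosen on all 10 | Leave-one-out, genes re-chosen in each fold (SD per study) | New patients |
|---|---|---|---|---|
| 5/5 | 100% | 100% | 38% (23 points) | 50% |
| 7/3 | 100% | 100% | 41% (15 points) | 50% |
| 8/2 | 100% | 100% | 47% (4 points) | 50% |

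With 5,000 or 20,000 genes and signatures of 1, 10 or 50 genes, the same-patient figure stays at 99.4 to 100% and the re-chosen figure ranges from 29 to 53%. As plain accuracy, the re-chosen figures for the 10-gene rule are 39%, 57 to 60% (depending on the run) and 76%, against 50%, 70% and 80% for calling everyone the majority class.

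**4. Limits of 10 patients.** Even 10 correct out of 10 *independent* patients has an exact 95% lower limit of 0.025^(1/10) = 69%. Leave-one-out cannot run at a 9/1 split, because omitting the one non-responder leaves a single class. The chance of at most one non-responder depends on the response rate, which is not given: at an assumed 80% it is 0.8^10 + 10 × 0.2 × 0.8^9 = 38%; at 70%, 15%; at 50%, 1%.

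**The case against.** **The plan never says it will build or score a signature.** This is correct, and it limits the point. A reader might infer from the table above that the trial will report a spuriously perfect predictor. The documents do not support that: Section 13.3 plans gene-level tests, no accuracy figure is named, and the nearest-centroid rule is only an illustration. The 100% result is conditional on someone scoring a signature in these patients, or cross-validating it after choosing genes on all 10.

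**The operative objective is association.** Section 3.1 is already close to the wording that the design can support, and the synopsis rationale, which spans several biologics, can be read as the goal of a wider programme. That reading does not cover the other two places. The synopsis primary objective includes prediction, and the sentence in Section 2 describes what will be done with this study's profiles.

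**It is a pilot, and a SAP will follow.** Both soften the point, and no treatment decision in the trial rests on a signature. But the pilot label is used to explain the sample size and does not limit the claim. The SAP is promised before final analysis, in an unblinded study, and nothing in the current text commits it to any form of validation.

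**Cross-validation at n = 10 is a weak remedy.** This stands. It is imprecise, can fall below chance and fails at 9/1. It guards against a misleading figure but does not make prediction feasible here.

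**Conclusion.** The concern holds as a mismatch between claim and design. The synopsis and Section 2 assign prediction to this study's data, while Section 3.1 and the analysis sections deliver association testing in one set of 10 patients. The predictive conclusion cannot be supported as planned.

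The size of the hazard rests on assumed gene numbers, independence and splits. The qualitative result is robust to them: noise scores about 100% in the patients used to choose the genes and about 50% balanced accuracy in new ones.

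Two stronger readings are not supported. One is that the plan itself sets out to report in-sample accuracy; it is silent. The other is that the phrase *initial analysis* in Section 13.6 implies a later cohort that could serve as a test set; none is described. The association objective in Section 3.1 is not faulted by this point. The change should be made, but its grade is should-fix, because the necessary correction is mainly to the stated claim.

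**What to change.** 1. **Synopsis (Rationale and Primary Objective) and Section 2.** Replace the prediction wording with *identify candidate genes associated with response*, in line with Section 3.1, and state that no predictive claim will be made from these 10 patients.

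2. **Section 13.3.** State that if any signature accuracy is reported:
   - gene selection and tuning are redone inside every leave-one-patient-out fold;
   - the result is labelled exploratory and shown beside the majority-class accuracy and a label-permutation p value (which at 8/2 cannot be below 1/45 = 0.022);
   - a note says that the estimate is very imprecise and can fall below chance at n = 10;
   - it is not computed if either response group has fewer than two patients;
   - no exact binomial interval is attached, because the folds share patients and are not independent.

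3. **Only if a later cohort is actually enrolled.** Lock the signature first, keep the new patients as an untouched test set and do not pool them with the first 10.

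Item 2 presupposes a stated PASI responder definition and time point, which the documents lack, and a responder comparison in place of, or beside, the diseased-versus-normal one in the synopsis.

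Cost: protocol and SAP wording and a few hours of computing, with no added patients or procedures. The downside is a weaker stated claim and a less favourable accuracy figure.
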